- Start the study only after all legal requirements in my country have been fulfilled.
- Obtain informed consent for all subjects prior to performing any study-related action.
- Permit study-related monitoring, audits, IEC/IRB review, and regulatory inspections and provide direct access to all study-related records, source documents, subject files, and case report forms for the monitor, auditor, IEC/IRB, or regulatory authority upon request.
- Use all study materials only as specified in the clinical study protocol.
- Report to the responsible product safety officer, within 24 hours, any serious adverse event (SAE), and serious adverse device effect (SADE), whether considered related or not related to the investigational device.
- Provide to the sponsor, prior to initiating the study, my curriculum vitae, including details of relevant experience and an explanation of any prior terminated research (if applicable). Provide written disclosure of any financial interest, in accordance with 21 CFR Part 54, and promptly update this information if changes occur during or within one year after study completion.

Furthermore, I understand that:

- Changes to this protocol must be made in the form of an amendment that has the prior written approval of Merz and any applicable IEC/IRB or regulatory authority.
- The content of the clinical study protocol is confidential and proprietary to Merz.
- Any deviation from the clinical study protocol may lead to early termination of the study site.

Principal Investigator (print name)

Date (dd-MMM-year)

Signature

PROTOCOL SYNOPSIS

Protocol Title	Evaluation of Pain with Belotero® Balance with Integral Lidocaine for Correction of the Nasolabial Folds
Protocol Number	M930021001
Active Product	Belotero® Balance with integral lidocaine
Comparator Product	Belotero® Balance
Study Phase	Device Pre-Market
Indication	Injection into the mid-to-deep dermis for correction of moderate-to-severe facial wrinkles and folds, such as nasolabial folds (NLF)
Number of Sites and Countries	This study will be conducted at up to three (3) study centers in the United States.
Number of Study Subjects	Approximately fifty-two (52) subjects will be enrolled and treated. Each NLF (i.e., right and left NLFs) will be analyzed separately for the primary and secondary endpoints, resulting in approximately 104 discrete units of measure.
Objectives	
Effectiveness
 
Demonstrate the effectiveness of Belotero Balance with lidocaine (Test group) for the reduction of injection-related pain in comparison to Belotero Balance without lidocaine (Control group) for the correction of NLFs. 
Safety
 
Identify and describe adverse events (AEs) and serious adverse events (SAEs) during the course of the study. Additionally, common treatment site responses (CTRs) will be assessed.
Key Endpoints	
Primary
 
Demonstrate a statistically significant, mean reduction in pain, measured using a 10-cm visual analogue scale (VAS), in the Test NLF compared to the Control NLF immediately after split-face NLF treatment (i.e., at time zero) on Day 1. Time zero will be defined as the time the last injection needle is removed from each NLF, separately, after a full correction on Day 1. 
Secondary
 
Compare the responder rates between the Test and Control NLFs, separately, at Week 6, as assessed live by the blinded evaluator and according to the Merz NLF Scale. Response is defined as \geq 1-point improvement on the Merz NLF Scale for each NLF compared to baseline. Each NLF is to be assessed separately. 
Safety
 
Evaluate the incidence and nature of device- and/or injection-related AEs and SAEs observed during the study. Additionally,

	
the incidence, severity, and duration of pre-specified CTRs will be evaluated using subject diaries.

Study Design Overview	
This is a 6-week, prospective, randomized, split-face, double-blind, multicenter, pre-market study to demonstrate the effectiveness of Belotero Balance with integral lidocaine (Test) for reduction of injection-related pain when compared to Belotero Balance without lidocaine (Control) for the correction of NLFs.
 
The split-face study consists of two treatment arms. Approximately 52 subjects will be randomized to receive treatment with Belotero Balance with integral lidocaine (Test product) in one NLF and Belotero Balance without lidocaine (Control product) in the contralateral NLF on Day 1. Randomization will also determine which NLF (subject's right or left) will be injected first. Subjects will be eligible for an optional touch-up treatment, at the investigator's discretion and to achieve optimal correction, at Week 2. Subjects will be followed for at least 4 weeks after the last injection.
 
Subjects enrolled will have a baseline rating of moderate to severe (i.e., rating of 2 or 3) on the Merz NLF Scale. Subjects must have the same Merz NLF Scale rating in both NLFs at the time of enrollment. A minimum of 20% of the enrolled subjects will be Fitzpatrick skin type IV, V, or VI. Subjects from the Fitzpatrick skin type IV, V, and VI group will be approximately evenly distributed within the IV, V, and VI categories.
 
The planned duration of participation for individual subjects is 6 weeks. For all subjects randomized at baseline, the study will consist of three office visits and a 72-hour post-treatment phone call. Additional effectiveness assessments include the blinded-evaluator Global Aesthetic Improvement Scale (GAIS), the subject GAIS, and two (2) FACE-Q assessments.

Key Inclusion/ Exclusion Criteria	
To be eligible for the study, each subject must meet all of the following criteria:
 
1. Has right and left NLF ratings of 2 or 3 (moderate or severe) on the Merz NLF Scale, as determined by the blinded evaluator.2. Has the same Merz NLF Scale rating on both NLFs (i.e., symmetrical NLFs).3. Is at least 18 years of age.4. Understands and accepts the obligation not to receive any other procedures (i.e., dermal fillers, toxin treatments, facial ablative or fractional laser, microderm abrasion, chemical peels, non-invasive skin-tightening [e.g., Ultherapy, Thermage], or surgical procedures) below the orbital rim on the face during study participation. 
Patients meeting any of the following criteria are not eligible to participate in the study:
 
1. Had prior surgery in the mid- and/or lower-face area, including the nasolabial fold(s), or has a permanent implant or graft in the mid- and/or lower-face area that could interfere with effectiveness assessments. (NOTE: Rhinoplasty is permitted if the procedure

	
was \geq 12 months prior to study enrollment.)
 
2. Has skin or fat atrophy, beyond typical for the subject's age, in the mid- to lower-facial region or has been diagnosed with a connective tissue disorder.3. Has unphysiological skin laxity or sun damage, beyond typical for the subject's age, or subject plans to tan during the study period.4. Has undergone oral surgery (e.g., orthodontia, extraction, implants) in the past 30 days or plans to receive such surgery during participation in the study.5. Has received mid- and/or lower-facial region treatments with porcine-based collagen fillers, Belotero® Volume, JUVÉDERM VOLUMA®, Restylane® Lyft, RADIESSE®, poly L-lactic acid (PLLA), or mesotherapy within the past 24 months and/or with other hyaluronic acid (HA) products within the past 12 months or plans to receive such treatment during participation in the study.6. Has ever been treated with fat injections or permanent and/or semi-permanent dermal fillers in the mid- and/or lower-facial region or plans to receive such treatment during participation in the study.7. Has received immunosuppressive medications or systemic steroids (except intranasal/inhaled steroids) in the past 2 months or plans to receive such treatment during participation in the study.8. Has an acute inflammatory process or infection at the injection site (e.g., skin eruptions such as cold sores, cysts, pimples, acne, eczema, hives, streptococcus infections) or history of chronic or recurrent infection or inflammation with the potential to interfere with study results or increase the risk of AEs.9. Has a history of allergic/anaphylactic reactions, including hypersensitivity to lidocaine or anesthetics of the amide type, hyaluronic acid preparations, gram positive bacterial proteins, or any of the device components.10. Has a known bleeding disorder or has received or is planning to receive anti-coagulation, anti-platelet, or thrombolytic medications (e.g., warfarin), anti-inflammatory drugs (oral/injectable corticosteroids or NSAIDs [e.g., aspirin, ibuprofen]), or other substances known to increase coagulation time (e.g., vitamins or herbal supplements, i.e., Vitamin E, garlic, gingko) from 10 days before injection to 3 days after injection.11. Has any other medical condition with the potential to interfere with study outcome assessments or compromise subject safety (i.e., increase the risk of adverse events).
--	--

Table of Contents

mL	Milliliter
N	Number of non-missing observations
NLF	Nasolabial fold
pH	Potential of hydrogen (quantitative measure of the acidity or basicity)
PI	Principal investigator
PLLA	Poly-L-lactic acid
PMA	Premarket approval

Abbreviation/Term	Definition
PPS	Per protocol set
SADE	Serious adverse device effect
SAE	Serious adverse event
SAP	Statistical analysis plan
SD	Standard deviation
SE	Standard error
SES	Safety evaluation set
SOC	System organ class
UADE	Unanticipated adverse device effect
US	United States
UV	Ultraviolet
VAS	Visual analogue scale
WHO	World Health Organization

1 INTRODUCTION

1.1 Background

Belotero Balance (Control product) was approved by the U.S. FDA in November 2011 (PMA Number: P090016) to help smooth moderate-to-severe facial wrinkles and folds, such as nasolabial folds (NLF), by temporarily adding volume to facial tissue and restoring a smoother appearance to the face. At present, the approved Belotero Balance formulation does not contain lidocaine hydrochloride. The investigational device (Test product) is a change to the approved Belotero Balance formulation to integrate 0.3% lidocaine hydrochloride for the purpose of pain reduction.

Notably, a formulation similar to Belotero Balance with lidocaine has been registered in approximately 32 countries worldwide since 2013 (brand names: Esthelis Basic Lidocaine, Belotero Basic Lidocaine).

1.2 Study rationale

During the administration of dermal fillers, pain is one of the most consistent patient complaints [1]. To mitigate patient pain and discomfort, lidocaine hydrochloride ($C_{14}H_{23}ClN_2O \times H_2O$, herein, lidocaine) is frequently used by healthcare providers prior to dermal filler injection or alternatively lidocaine is mixed directly into the product [2][3][4].

Lidocaine is one of the most widely used anaesthetic drugs in the world. Although its activity as a membrane-stabilizing agent has made it useful as an anti-arrhythmic drug, the most common application of lidocaine is as a local anaesthetic. It is available as injectable solution and in topical formulations. The compound was first synthesized in 1943 and commercialized by Astra AB in 1948; this amide type anaesthetic has a long history of safe and effective use [5].

The safety profile of lidocaine is well characterized [6]. Toxicity is modest, with cited LD50 values from 159-773 mg/kg in rats and 105 mg/kg (intraperitoneal injection) in mice. The recommended maximum dosage in adults or children is 4.5 mg/kg or 300 mg/session. While serious side effects, including respiratory failure and cardiac arrest, have been observed at high doses, especially following intravenous administration, side effects following peripheral injection at the recommended dosage are modest and include dizziness, tinnitus, drowsiness, and sensation of heat, cold, or numbness. Although allergic reactions to lidocaine have been documented, they have been reported as being “extremely rare”. Buffering the pH of lidocaine solutions near physiological pH, but below pKa of ~7.85, improves both safety and efficacy, since lidocaine hydrochloride is more soluble than lidocaine base, and buffered lidocaine solutions are less painful at injection than unbuffered solutions [7][8].

The pharmacokinetics profile of lidocaine has been extensively studied in both humans and animal models. In humans, the majority (up to 70%) of lidocaine is metabolized in the liver, with the metabolites excreted in the urine. Lidocaine levels in the blood follow a biphasic exponential curve, with an initial half-life of 8 to 17 minutes in the first 10 to 15 minutes after intravenous injection followed by a half-life of 87 to 108 minutes for the remainder of the degradation time in humans. Lidocaine diffuses rapidly through tissue, reaching peak plasma concentration only 17 minutes after intranasal administration in rats.

Pairing its efficacy with an extensive physician experience, lidocaine is frequently the anaesthetic of choice in facial aesthetic applications and has been incorporated into products such as Artefill[®], Prevelle[®] Silk, Restylane-L[®], Radiesse[®] (+), and JUVÉDERM[®] Ultra, all at the 0.3% concentration.

Literature on the effectiveness and safety of lidocaine in various facial aesthetic applications, accompanied by its use in other similar products, justifies the need for Merz North America, Inc. to conduct a robust randomized clinical trial to demonstrate the effectiveness of Belotero Balance with lidocaine (Test product) for reduction of injection-related pain when compared to FDA-approved Belotero Balance without lidocaine (Control product) for the correction of nasolabial folds. The investigational device (Test product) is a change to the approved Belotero Balance formulation to integrate 0.3% lidocaine hydrochloride for the purpose of pain reduction.

1.3 Potential benefits and risks

The potential benefit of Belotero Balance with integral lidocaine (Test product) is the reduction of injection-related pain when using dermal fillers to correct the NLFs.

Adverse events have been identified during post-approval use of Belotero Balance (Control product); however, because the events are reported voluntarily, from a population of uncertain size, it is not always possible to reliably estimate their frequency or establish a causal connection to Belotero Balance. The following adverse events have been chosen for inclusion due to a combination of their seriousness, frequency of reporting, or potential causal connection to Belotero Balance: allergic reactions including Quincke's edema, anaphylaxis, rash, hives, necrosis, inflammation, granuloma, indurations, and/or nodules; hematoma; Tyndall effect; Cordon-like effect; bumps; pustule, scarring; swelling; erythema; pain; edema; bruising; lumps; discoloration; infection; migration/displacement; asymmetry; numbness; vascular occlusion; and/or visual disturbance.

Potential adverse events associated with the use of Belotero Balance Lidocaine (Test product) include: induration (transient or permanent); bump (transient or permanent); nodule (transient or permanent); lump (transient or permanent); blister; edema/swelling; erythema/redness; rash; bleeding; hematoma; pain; itching/pruritus; tingling; numbness;

burning sensation; hyperpigmentation; hypopigmentation; Tyndall effect; inflammation; Type I allergy; Type IV allergy; superficial local infection; severe deep local infection; severe systemic infection; chronic infection; necrosis; scarring; severe vascular compromise; transmissible severe systemic disease; fever; granuloma; cardiovascular compromise (e.g., loss of consciousness, palpitations, nausea, vomiting); embolization; sweating; nausea; paralysis; organ damage; nervous system impairments (e.g., dizziness, paraesthesia); worsening of a pre-existing condition; headache/cephalgia; severe visual impairment/blindness; nonthrombotic embolism; discoloration; scarring; transient vascular compromise; and/or death.

For both the test and control products, an additional harm or risk, which is not an adverse event, includes disappointment due to lack of or reduced performance and/or undesirable aesthetic effect.

Rare but serious adverse events associated with the intravascular injection of soft-tissue fillers in the face have been reported and include: temporary or permanent vision impairment; blindness; cerebral ischemia or cerebral hemorrhage, leading to stroke; skin necrosis; abscesses; granulomas; and damage to the underlying facial structures. Implantation of Belotero Balance into the vasculature may lead to embolization, occlusion of the vessels, ischemia, or infarction.

Lidocaine is commercially available and frequently used as a local and regional anesthetic agent. Potential side effects anticipated with its use include: lightheadedness; nervousness; apprehension; euphoria; confusion; dizziness; drowsiness; ringing noise in the ears; blurred or double vision; vomiting; sensations of heat, cold or numbness; twitching; tremors; convulsions; unconsciousness; respiratory depression and arrest; slow heartbeat; hypotension; and/or cardiovascular collapse, which may lead to cardiac arrest.

2 STUDY OBJECTIVES AND ENDPOINTS

2.1 Objectives

2.1.1 Effectiveness

The primary objective of the study is to demonstrate the effectiveness of Belotero Balance with lidocaine (Test product) for the reduction of injection-related pain in comparison to Belotero Balance without lidocaine (Control product) for the correction of NLFs.

2.1.2 Safety

The safety objective includes the identification and description of adverse events (AEs) and serious adverse events (SAEs) during the course of the study. Additionally, common treatment site responses (CTRs) will be assessed.

2.2 Endpoints

2.2.1 Primary endpoint

Demonstrate a statistically significant, mean reduction in pain, measured using a 10-cm visual analogue scale (VAS), in the Test NLF compared to the Control NLF immediately after split-face NLF treatment (i.e., at time zero) on Day 1. Time zero will be defined as the time the last injection needle is removed from each NLF, separately, after a full correction on Day 1.

2.2.2 Secondary endpoint

Compare the responder rates between the Test and Control NLFs, separately, at Week 6, as assessed live by the blinded evaluator according to the Merz NLF Scale. Response is defined as ≥ 1 -point improvement on the Merz NLF Scale for each NLF compared to baseline. Each NLF is to be assessed separately. The blinded evaluator is a qualified healthcare practitioner, delegated by the treating investigator.

- [REDACTED]

2.2.4 Safety endpoints

- Incidence and nature of device- and/or injection-related AEs and SAEs observed during the study.
- Incidence, severity, and duration of pre-specified CTRs reported in subject diaries.

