6 STUDY DEVICE AND TREATMENT OF SUBJECTS

6.1 Description of the study devices

6.1.1 *Test product*

The investigational device is a change to the Belotero Balance formulation to integrate 0.3% lidocaine hydrochloride for the purpose of pain reduction. Belotero[®] Balance with integral lidocaine is a sterile, bioresorbable, non-pyrogenic, viscoelastic, clear, colorless, homogeneous gel device. It is a bacterially fermented, injectable, hyaluronic-acid-based dermal filler. After extraction and purification, hyaluronic acid, manufactured from streptococcal cultures, is cross-linked with a binding agent 1,4-butanediol diglycidyl ether (BDDE) in two consecutively executed reactions and reconstituted in a physiologic buffer at pH 7 and concentration of 22.5 mg/mL.

Belotero Balance with integral lidocaine injectable implant will be supplied by the study sponsor. This product should be stored at room temperature (up to 25°C/77°F), away from heat, and should not be refrigerated. The test product has a clear, colorless (transparent) appearance. In the event that the syringe contains material that is not clear, do not use the syringe and notify the study sponsor.

6.1.2 *Control product*

Belotero[®] Balance is a sterile, bioresorbable, non-pyrogenic, viscoelastic, clear, colorless, homogeneous gel device. It is a bacterially fermented, injectable, hyaluronic-acid-based dermal filler. After extraction and purification, hyaluronic acid, manufactured from streptococcal cultures, is cross-linked with a binding agent, 1,4-butanediol diglycidyl ether (BDDE), in two consecutively executed reactions and reconstituted in a physiologic buffer at pH 7 and concentration of 22.5 mg/mL. Belotero[®] Balance is indicated for injection into the mid-to-deep dermis for correction of moderate-to-severe facial wrinkles and folds, such as nasolabial folds. The Belotero Balance Premarket Approval (PMA) submission (P090016) was approved November 14, 2011 by the Food and Drug Administration (FDA). Belotero filler had been previously approved for aesthetic use in the United Kingdom, Germany, Italy, Russia, Austria, and Switzerland. Currently, the approved Belotero Balance formulation does not contain lidocaine hydrochloride. The Belotero Balance package insert is included in [Appendix 11.2](#).

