7.2.2 Determining causal relationship

An AE is considered to be “related” to the investigational medical device if a causal relationship between the investigational medical device and the AE is at least a reasonable possibility (i.e., the relationship cannot be ruled out).

NOTE: The expression “reasonable causal relationship” is intended to convey that there are facts (evidence) or arguments to suggest a causal relationship. Otherwise, the relationship should be considered as “not related”.

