7.2 Safety Variables

All safety analyses will be performed on the SES.

AEs will be coded according to the Medical Dictionary for Regulatory Activities (MedDRA, version 20.0). Only treatment emergent adverse events (TEAEs) will be analyzed, which are defined as AEs with onset or worsening after the administration of the study drug. Incidences will be calculated for TEAEs on the system organ class level and on the preferred term level (total, by intensity, and by relationship – related or not related). Listings and tables displaying incidences for TEAEs leading to discontinuation and serious TEAEs will also be provided.

TEAEs associated with NLFs will be summarized by treatment. All TEAEs will be summarized without by-treatment breakdown.

In summaries by system organ class and preferred term each subject will be counted once per preferred term and treatment if applicable. Similarly in summaries by system organ class each subject will be counted once per system organ class and treatment if applicable. In summaries that are additionally broken down by intensity or relationship, subjects with multiple events will be summarized by the worst severity or worst relationship, as applicable.

Number and percentage of subjects with CTR, as well as the number of continuous CTR episodes, will be summarized by treatment and maximum severity as well as by treatment and maximum duration. Duration will be classified as 1-3 days, 4-7 days, 8-14 days 15-30 days and > 30 days.

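### The safety endpoint covers events related to the device or to the injection, but the causality rule tests only the device, so events attributed to the injection alone are counted as not related

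*Protocol*

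**What the plan says.** The first safety endpoint in Protocol 2.2.4 is the "Incidence and nature of device- and/or injection-related AEs and SAEs observed during the study". SAP 6.2 repeats it, and the Protocol synopsis and the safety objective in SAP 3.2.2 use the same two-part wording, so the reference to injection looks deliberate.

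The only rule for judging causality is Protocol 7.2.2. An AE is related "if a causal relationship between the investigational medical device and the AE is at least a reasonable possibility", which the same sentence explains as meaning that "the relationship cannot be ruled out". A note then says that there should be evidence or arguments for a causal link. It closes with "Otherwise, the relationship should be considered as" not related.

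On data collection, Protocol 7.2.4.1 lists a single causal-relationship item among the minimum AE data. The minimum SAE information in 7.2.4.2 asks for causality of the investigational device.

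On analysis, Protocol 8.4.2.1 speaks of relationship to the study device, by Test and Control. SAP 7.2 splits TEAEs into related and not related without saying to what, and adds that "TEAEs associated with NLFs will be summarized by treatment".

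**The concern.** The endpoint has two causal parts and the rule that feeds it has one. The SAP's related / not related split is the only visible route to the endpoint. Nothing in either document defines an injection-related event, requires it to be recorded, or says how to derive it. If sites follow 7.2.2 as written, the reported incidence leaves out part of what the endpoint claims to count, and the table gives no sign of it.

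A second looseness sits on top. Protocol 1.1 says "The investigational device (Test product) is a change to the approved Belotero Balance formulation", and 1.2 and 6.1.1 use the term in the same way, so the investigational device there is the Test product. Section 6.1, however, describes both products as study devices, and 8.4.2.1 uses that wider term for the analysis. The causality question and its tabulation therefore do not clearly refer to the same object.

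At stake is whether the reported related-event incidence means what the endpoint says, in a pre-market study where that incidence is a stated safety result.

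**Working it through.** The plan gives no figure for this point, so the check sets the texts side by side.

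**Step 1: which causes the protocol distinguishes.** Section 7.1.2, in defining an AE, lists events related to the investigational device or the comparator, and separately events related to the procedures involved. So the protocol itself treats product and procedure as different causes, and treats the comparator as something other than the investigational device.

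**Step 2: which causes each text covers.**

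| Place | Product | Injection procedure |
|---|---|---|
| Endpoint, Protocol 2.2.4 and SAP 6.2 | yes | yes |
| AE definition, Protocol 7.1.2 | yes, comparator named separately | yes |
| Causality rule, Protocol 7.2.2 | investigational device | not mentioned |
| AE minimum data, Protocol 7.2.4.1 | one item, object not named | not mentioned |
| SAE minimum data, Protocol 7.2.4.2 | investigational device | not mentioned |
| Analysis, Protocol 8.4.2.1 | study device | not mentioned |
| Analysis, SAP 7.2 | object not named | not mentioned |

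**Step 3: what happens to an event.** Take the investigator's view of each cause in turn.

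| Product a reasonable possibility | Injection a reasonable possibility | In the endpoint | Class under 7.2.2 | Agree |
|---|---|---|---|---|
| yes | no | yes | related | yes |
| yes | yes | yes | related | yes |
| no | yes | yes | not related | **no** |
| no | no | no | not related | yes |

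One of the four combinations disagrees, and always in the same direction: the rule can undercount the endpoint but cannot overcount it.

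**Step 4: how large the third row is.** The documents give no event rates or attribution frequencies, so no number can be put on it. It can be bounded: the shortfall cannot exceed the number of TEAEs classed as not related. Whether the row is nearly empty depends on how a site reads 7.2.2. If an event is related whenever "the relationship cannot be ruled out", an event for which gel and needle cannot be told apart is related, and only events with the product positively excluded fall in the row. If a site works from the note and looks for positive evidence against the product, more events fall in it.

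**Step 5: which device the rule refers to.** Section 7.2.2 uses the term that 1.1, 1.2 and 6.1.1 attach to the Test product. Section 7.1.1 gives a generic definition, any device being assessed in the investigation, which could take in both products. Section 8.4.2.1 uses the wider term. The texts do not agree, but none of them says that events in the Control fold are to be classed as not related.

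**The case against.** The strongest reply is that the gap hardly matters in practice, and much of it stands.

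- *Inclusive threshold.* A site reaction after a filler injection can rarely be blamed on the needle with the gel excluded. Protocol 7.1.3 ties an adverse device effect to use of the device, the needles come in the product kit (6.4), and 1.3 lists haematoma and pain among the events associated with the products. Most puncture effects would therefore probably be called related. This limits the size. It does not supply the missing rule: 7.1.3 does not amend 7.2.2, and the SAP tabulates related and not related, not adverse device effects.
- *Nothing is lost from the totals.* TEAEs associated with the folds are tabulated by treatment whatever their relatedness, and the diary CTRs, which are the second safety endpoint, pass through no causality filter. This is correct. But total TEAEs do not answer an endpoint defined by relatedness.
- *No bias between folds is shown.* Also correct. The omission applies to both folds in the same way, and the effectiveness analyses are not involved.

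Two stronger readings are tempting. A reader might infer from 7.2.2 and 6.1.1 together that the Control fold must show no related events at all. The documents do not support that. The treating investigator is blinded to which fold is which (3.1, 6.7) and cannot apply a Test-only rule by fold, and the analysis text refers to the study device for both groups. A reader might also infer that the attribution could not be recovered after database lock. That is not shown either: the list in 7.2.4.1 is expressly a minimum, the eCRF is not among the documents, and event location and dates are required, which would support a later medical review.

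**Conclusion.** The point holds in a limited form. As written, an event attributed to the injection alone, with the product ruled out, is part of the safety endpoint and is counted as not related. This is more than missing detail, because following the stated rule gives a count that differs from the stated endpoint. The size cannot be quantified from the documents. It is probably small, it can occur in either fold, and it does not touch total TEAE or CTR results. The inconsistent use of investigational device and study device is a wording fault to correct at the same time, not evidence that Control-fold events would be misclassified.

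This rests on two assumptions: that the related / not related table in SAP 7.2 is how the endpoint will be reported, since no other derivation is given, and that the eCRF and its instructions add no injection attribution beyond the protocol's minimum list. If the eCRF already has such an item, only the definition and the SAP derivation remain to be written. The change should be made, but it does not threaten the trial's main conclusion.

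**What to change.** - **Protocol 7.2.2 and 7.2.4.1:** assess each AE for relationship to the study product in the affected fold (Test or Control, with the assessor blinded) and, separately, to the injection procedure. For an event not tied to a fold, ask about either study product. Carry the same two questions into the SAE minimum data in 7.2.4.2.
- **Terminology:** use study product, or study device, for both Test and Control wherever causality is assessed or tabulated.
- **SAP 7.2:** define an endpoint event as one related to the product or to the injection, and tabulate the combined count and the two attributions.

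If a second item is not wanted, the minimum is one sentence in 7.2.2 stating that related means related to either study product or its injection, with a matching line in SAP 7.2. That aligns rule and endpoint but cannot separate product effects from needle effects.

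The full version costs one extra eCRF item, a few sentences of text and a little more work for sites. It is easiest while investigators are still assessing events, because a later change would need past events to be reassessed.
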